
Study Procedures Continued
	
administered during dialysis treatments and subjects remain fasting for the duration of the breath test collection.
 
Consumption of the following drugs that may interfere with (compete with or induce) the metabolism of C-Methacetin will be recorded on the case report forms and include the following:
 
 
a. HMG-CoA reductase (Statin) drugs in the 30 days prior to study enrollment;
 
b. Acyclovir and famotidine taken in the 48 hours prior to study enrollment; and
 
c. Any of the following taken during the study period: allopurinol, carbamazepine, cimetidine, ciprofloxacin, daidzein, disulfiram, Echinacea, enoxacin, fluvoxamine, methoxsalen, mexilitene, montelukast, norfloxacin, phenylpropanolamine, phenytoin, propafenone, rifampin, terbinafine, ticlodipine, thiabendazole, verapamil, zileuton or oral contraceptives.
 

Safety Evaluations
	
This is not a therapy trial; however, the safety of administration of C-Methacetin solution in this setting will be evaluated. Safety assessments will be performed by assessing for acetaminophen levels and levels of acetaminophen-Cys adducts, by collecting daily serum samples for adduct and APAP testing in the laboratory of [name], University of Arkansas for Medical Sciences, Little Rock, AR, on the first 20 evaluable ALF patients.

Safety Analysis
	
The detection of serum APAP-Cys adducts in those ALF patients not thought secondary to APAP toxicity will be considered significant if a value > 1.0 nmol/L is determined. Likewise, the detection of any level serum APAP in these patients will also be considered significant. An increase of significance in the adduct level in APAP cases or in serial serum APAP levels will also require adjudication as a possible indicator of an additional adverse effect of C-Methacetin administration. In addition, standard laboratory parameters including serum electrolytes and Liver biochemistries will be measured in all subjects through a maximum of 7 days (See Schedule of Assessments, Section 8.5).

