LD50 values of 1190mg/kg were administered, the Methacetin dose administered in human breath tests in adults of 75 mg, or approximately 1mg/kg, has a safety ratio in excess of 1000-fold (11). There have been no reports of any complications with the use of this substance in over 2500 patients tested worldwide (see IDE filing). The main metabolite of Methacetin is acetaminophen which has wide routine clinical use at much higher doses than orally administered dose of C-Methacetin of 75mg used in this study. Testing of sera after exposure to 75mg C-Methacetin in 23 ALF patients at King's College disclosed no increase in serum acetaminophen-cysteine adducts that would suggest further hepatocyte injury due to the C-Methacetin (12).

Many studies using C-Methacetin for liver function assessment have been published. Representative references have been cited that support the conclusion that C-Methacetin solution is a "safe" test substrate and that it has been used on high-risk population groups such as the elderly, neonates or pregnant women, and patients with cirrhosis (13-16). This provides further assurance that C-Methacetin is appropriate to use in breath tests intended for liver function assessment.

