### 4.2.3 Safety Endpoints

The administration of Methacetin (75mg/dose) results in the generation of acetaminophen (75mg/dose), and therefore presents a modest safety concern in patients with ALF, particularly in those with APAP overdose. Use of NAC in patients admitted with APAP overdose or non-APAP ALF should obviate minor adverse effect potential of this small dose. In a retrospective study, sera from ALF patients who were given the C-Methacetin MBT at King's College were assayed for presence of acetaminophen adducts. Participants of this study received MBT daily up to 7 days. No *de novo* appearance of adducts was observed for non-APAP subjects, nor was there an increase in adduct levels in acetaminophen toxicity subjects.

To confirm the safety profile of the MBT, a prospective safety sub-study is planned for this protocol as outlined in Section 10.1. This safety sub-study will include determining APAP and APAP-adduct concentrations in sera from study participants with ALF immediately prior to each administration of the C-Methacetin solution. A positive safety endpoint is defined as:

1. the absence of decline in APAP or APAP-adduct concentration between two consecutive determinations for patients with ALF due to APAP overdose;
2. presence of a significant (toxic quantity,  $\geq 1 \mu\text{mol/L}$ ) APAP-adducts in patients with non-APAP ALF;
3. adjudicated cases where APAP (non-adduct, parent compound) is detected in the serum of a patient with non-APAP ALF. It should be noted that in some instances, APAP appears to be detected in patients with non-APAP ALF if the total bilirubin is  $\geq 10 \text{ mg/dl}$ ; these are considered false-positive due to the cross-reactivity between APAP reactants and bilirubin in some colorimetric APAP assays (Polson, et al.). Such cases of detectable APAP in patients with non-APAP ALF will be adjudicated on an individual basis by the study's appointed

independent Medical Safety Monitor to determine the likelihood of Methacetin toxicity. Results of adduct testing will initially be reviewed internally and forwarded in real time to the MSM for review. These data will then be reported in summary fashion to the DSMB.

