#### **8.3 Performance of the APAP Adduct Assays and APAP Concentration Assays**

Serum for acetaminophen (APAP) and APAP-adduct levels will be collected with routine morning labs on each day from Day 2-7, as well as Day 1 as a baseline value, from the first 20 ALF subjects enrolled. Serum samples will be reserved for the sole purpose of determining whether APAP or APAP-adducts accumulate during repeated administrations of the C-Methacetin solution in patients with ALF. The collected samples will be shipped to and analyzed by [name] at the University of Arkansas.

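### Safety endpoint item 1 counts two successive undetectable APAP values as positive on its plain reading, and the sampling days that define its consecutive pairs conflict

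*Combined protocol and SAP*

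**What the plan says.** Section 4.2.3 lists three ways to reach a positive safety endpoint, where positive means a possible harm signal. Item 1 covers patients whose acute liver failure is due to APAP overdose: "the absence of decline in APAP or APAP-adduct concentration between two consecutive determinations for patients with ALF due to APAP overdose". It gives no quantification limit for either assay and no rule for equal or undetectable values. Detectability is discussed only in item 3 and in the Synopsis, both for patients whose failure is not due to APAP.

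On sampling, the Synopsis (Safety Evaluations) says the assessment is made "by collecting daily serum samples for adduct and APAP testing". Sections 8.3 and 10.1 both specify a Day 1 baseline and then every day from Day 2 to Day 7. The schedule in Section 8.5 marks the APAP and adduct row on Days 1, 2, 3, 5 and 7 and has no column for Day 4 or Day 6. Section 4.2.3 says that both concentrations are determined "in sera from study participants with ALF immediately prior to each administration" and refers to Section 10.1 for the sub-study.

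**The concern.** An endpoint based on failure to decline works only while there is something left to decline. Once APAP is undetectable, the next value cannot be lower, so on the either-analyte reading every later pair is positive by construction. The count then combines two groups. Some patients have cleared the drug. Others have a measurable level that has stopped falling, and only these bear on whether the test substrate adds exposure.

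Item 1 also works on consecutive determinations, so the sampling calendar is part of its definition. Two calendars give different pairs, different intervals and different dose exposure within a pair. The same patient could be positive under one and negative under the other. At stake is whether a tabulation of item 1 can be read at all in the patients whom Section 4.2.3 names as the particular concern.

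**Working it through.** The plan gives no rate, limit or sample-size figure for item 1, so there is none to reproduce. The check counts pairs and then applies the rule to two constructed series.

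**Inputs.** Breath tests, and so doses, fall on Days 1, 2, 3, 5 and 7 (Sections 5.1 and 8.2). Samples are taken as pre-dose (Section 4.2.3; Section 8.2.1 also puts protocol laboratory work before the substrate). Sampling days are as set out above.

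**Pairs per analyte**

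| Calendar | Consecutive pairs | Doses between the two samples |
|---|---|---|
| Section 8.5: Days 1, 2, 3, 5, 7 | 1-2, 2-3, 3-5, 5-7 (4 pairs) | 1, 1, 1, 1 |
| Synopsis, 8.3, 10.1: Days 1 to 7 | 1-2, 2-3, 3-4, 4-5, 5-6, 6-7 (6 pairs) | 1, 1, 1, 0, 1, 0 |

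With either analyte sufficient, a patient with all samples has 2 × 4 = 8 or 2 × 6 = 12 comparisons. With both required in the same pair, there are 4 or 6.

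**Two hypothetical patients** (Days 1 to 7, arbitrary units, 0 = undetectable; only the order of the values matters)

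- Patient A, drug cleared: APAP 40, 20, 8, 0, 0, 0, 0; adduct 10, 8, 6.5, 5, 4, 3.2, 2.5.
- Patient B, brief measurable plateau: APAP 64, 32, 16, 8, 4, 2, 1; adduct 10, 8, 6, 6, 4.5, 3.5, 2.5.

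A pair is positive if the later value is not below the earlier one.

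| Rule | A, five days | A, daily | B, five days | B, daily |
|---|---|---|---|---|
| Either analyte | 1 | 3 | 0 | 1 |
| Both analytes | 0 | 0 | 0 | 0 |
| Either analyte, pairs with both values below quantification excluded | 0 | 0 | 0 | 1 |

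Patient A is positive only through APAP going from 0 to 0: pair 5-7 on the five-day calendar, and pairs 4-5, 5-6 and 6-7 on the daily one. Two of those three daily pairs (4-5 and 6-7) have no dose between the samples. Patient B is positive only at pair 3-4, which does not exist on the five-day calendar, where the adduct falls from 6 on Day 3 to 4.5 on Day 5.

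The quantification rule removes all of patient A's positives and keeps patient B's plateau. It does not resolve the calendar: patient B still changes status with the sampling days.

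**The case against.** The best defence has four parts.

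- A broad safety screen is a legitimate choice, and the plain sense of the wording is that either analyte suffices. That is the likelier reading. The negated phrase also permits the sense that neither declines, and a few words would settle it. Breadth does not explain why a cleared patient should count.
- A reviewer looking at so few series would recognise two undetectable results. Section 4.2.3 adds: "Results of adduct testing will initially be reviewed internally and forwarded in real time to the MSM for review". This limits the practical harm. The sentence names adduct results, however, and patient A's problem lies in parent APAP. The definition should not depend on later judgement.
- The Section 8.5 table has columns only for breath-test days. It also omits Days 4 and 6 for laboratory tests that Section 8.4 wants daily, so this is a general gap in the table. That is fair, but the text and the table still disagree about which samples exist.
- The Manual of Procedures might cover this. It is not available here, and the protocol does not cite it for this endpoint or these assays.

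Two stronger readings are tempting. First, a reader might infer that the plan contradicts itself by looking for a rise elsewhere. The Synopsis says "An increase of significance in the adduct level in APAP cases or in serial serum APAP levels will also require adjudication", Section 8.3 keeps the samples "for the sole purpose of determining whether APAP or APAP-adducts accumulate during repeated administrations", and earlier results are reported as "nor was there an increase in adduct levels in acetaminophen toxicity subjects" (Section 4.2.3) and "disclosed no increase in serum acetaminophen-cysteine adducts that would suggest further hepatocyte injury" (Section 3.3.3). The documents do not support a contradiction. Every rise is also a failure to decline, so the Synopsis names a subset for adjudication. Section 10.1 restates the purpose of the samples neutrally, as determining levels. The no-increase statements report a completed retrospective study and set no criterion for this one.

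Second, the pre-dose wording in Section 4.2.3 might look like a third calendar. It does not exclude other samples, and it points to Section 10.1, which is daily.

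**Conclusion.** The point holds and is minor. As worded, and on its plain either-analyte reading, item 1 turns clearance of APAP into a positive safety endpoint. The protocol also gives two calendars, with 4 or 6 consecutive pairs per analyte. The pair counts rest on the stated sampling and dosing days, with samples taken before dosing and none missed. The patient series are constructed and show only that status can change with choices the text leaves open.

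A reader might go on to infer that the sub-study will produce many false positives. The documents do not allow that conclusion. They give no half-life, assay precision, quantification limit or number of APAP cases among the 20 patients, so no frequency can be derived. The effect is confined to interpreting item 1 in the APAP-overdose cases of that sub-study. No stopping rule in the documents rests on item 1, and the primary analysis is untouched.

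**What to change.** Three wording changes, settled before the sub-study data are reviewed:

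- (a) In Section 4.2.3, state that a pair in which both values of an analyte are below that assay's lower limit of quantification is not an event for that analyte.
- (b) In the same item, say explicitly whether non-decline in one analyte is enough or both are required.
- (c) Reconcile the sampling days in Section 8.5 with the Synopsis and Sections 8.3 and 10.1, and say whether a pair with no administration between its samples counts. Which calendar applies is for the sponsor to decide.

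The cost is drafting only. Change (a) loses no measurable plateau. If (b) is settled as both analytes, a plateau in one analyte such as patient B's no longer counts, and the protocol should disclose that loss of sensitivity. If daily sampling is kept and pairs with no intervening dose are excluded, 2 of the 6 daily pairs per analyte are given up and a delayed rise could be missed.

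### In APAP-overdose ALF, safety endpoint item 1 compares the change in APAP or adducts with zero instead of an expected decline, so a slowed fall is not flagged and assay noise can be

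*Combined protocol and SAP*

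**What the plan says.** Section 4.2.3 notes that each breath test generates acetaminophen ("The administration of Methacetin (75mg/dose) results in the generation of acetaminophen (75mg/dose") and names APAP-overdose patients as the particular concern. For them, item 1 makes the endpoint positive on "the absence of decline in APAP or APAP-adduct concentration between two consecutive determinations for patients with ALF due to APAP overdose". For non-APAP ALF, item 2 uses an absolute level: "presence of a significant (toxic quantity", set at 1 µmol/L or more. The synopsis, for the same non-APAP group, says adducts "will be considered significant if a value > 1.0 nmol/L is determined". For APAP cases the synopsis adds: "An increase of significance in the adduct level in APAP cases or in serial serum APAP levels will also require adjudication". It does not define the size of such an increase.

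The retrospective King's College data are summarised in 4.2.3 as no new adducts in non-APAP subjects, "nor was there an increase in adduct levels in acetaminophen toxicity subjects".

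Sampling is described in three ways. Section 8.3 says serum "will be collected with routine morning labs on each day from Day 2-7, as well as Day 1 as a baseline value", and 10.1 agrees. The schedule in 8.5 marks serum only on Days 1, 2, 3, 5 and 7. Section 4.2.3 has it drawn "immediately prior to each administration of the" test solution, which also means the dosing days. The sub-study covers the first 20 ALF subjects. The number with APAP aetiology is not stated, there is no untreated comparator, and section 12 describes no analysis of these data.

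**The concern.** Treating a failure to decline as the harm signal presupposes that APAP and adducts from the overdose fall on their own. The relevant comparison is then with the fall expected without methacetin. Item 1 compares with zero instead. It responds reliably only when the methacetin contribution outweighs natural elimination over an interval, and it has no reference rate, margin or bound. The synopsis rule on increases is also a net-change rule and does not close the gap. The retrospective statement about overdose subjects has the same limitation.

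The rule can also err in the other direction. When the natural fall between samples is small, assay error alone can make a later value equal or exceed the earlier one. Once a level is undetectable on two consecutive samples there is, read literally, no decline.

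Section 8.3 reserves the sera for finding out whether APAP or adducts accumulate. At stake is whether that question can be answered in the group of most concern.

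**Working it through.** The plan gives no figure to reproduce here, so this is a calculation of what item 1 can and cannot see.

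**Inputs from the protocol.** Doses on Days 1, 2, 3, 5 and 7 (5.1), so dosing-day samples are Δ = 1 or 2 days apart. Daily samples (8.3, 10.1) would add the dose-free intervals Day 4–5 and Day 6–7.

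**Assumptions, not in the documents.** First-order decline, half-life T of 0.5 to 7 days, baseline adduct level C0 of 1 to 20 µmol/L.

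**Step 1: what one interval can hide.** Without methacetin the second value is C0 × 2^(−Δ/T). Apart from assay error, item 1 stays negative for any contribution h at the second sample with h < C0 × (1 − 2^(−Δ/T)). The baseline above which 1 µmol/L can be hidden is 1 / (1 − 2^(−Δ/T)).

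| T (days) | Share of C0 hidden, Δ=1 | Break-even C0, Δ=1 (µmol/L) | Share hidden, Δ=2 | Break-even C0, Δ=2 (µmol/L) |
|---|---|---|---|---|
| 0.5 | 75% | 1.33 | 94% | 1.07 |
| 1 | 50% | 2.00 | 75% | 1.33 |
| 2 | 29% | 3.41 | 50% | 2.00 |
| 3 | 21% | 4.85 | 37% | 2.70 |
| 5 | 13% | 7.73 | 24% | 4.13 |
| 7 | 9% | 10.61 | 18% | 5.57 |

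Example: C0 = 10, T = 2, Δ = 1. The expected value is 10 × 2^(−1/2) = 7.07. With h = 2 the value is 9.07, a 9.3% decline, and item 1 is negative. At C0 = 1 the hidden amount is always below 1 µmol/L.

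**Step 2: a whole course.** Recursion L(k+1) = L(k) × 2^(−1/T) + d(k). Here d = 1 µmol/L for the intervals that follow a dose (Days 1–2, 2–3, 3–4, 5–6) and 0 for Days 4–5 and 6–7. Assay error is lognormal with an assumed CV of 10%. A patient is flagged if any value is at least the preceding one.

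For C0 = 10 and T = 2 the error-free path is 10, 8.07, 6.71, 5.74, 4.06, 3.87, 2.74, so it falls every day. Without methacetin Day 7 would be 10 × 2^(−3) = 1.25, and 2.74 / 1.25 = 2.2.

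| C0 | T (days) | Missed, daily samples | Missed, 8.5 days | Day 7 level relative to no methacetin |
|---|---|---|---|---|
| 10 | 1.5 | 50% | 96% | 2.8 |
| 10 | 2 | 44% | 84% | 2.2 |
| 20 | 1.5 | 84% | 99% | 1.9 |
| 20 | 2 | 75% | 94% | 1.6 |

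In all four cases the error-free path falls throughout, so every detection comes from assay error. At C0 = 5 with daily samples the rule mostly works (12% or fewer missed).

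**Step 3: no methacetin effect.** With d = 0, daily samples and the same assay error, about 28% of patients are flagged at T = 3 days and 54% at T = 4 days. The rate is lower at shorter half-lives.

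**The case against.** The strongest reply is that item 1 does not stand alone. Item 2 covers non-APAP patients in the same sub-study, where no overdose background masks anything. If each dose added 1 µmol/L in them, item 2 would be reached after one or a few doses. Section 4.2.3 also reports no new adducts in non-APAP subjects tested daily for up to 7 days. All adduct results go to the Medical Safety Monitor, the synopsis requires adjudication of increases, and AEs and SAEs are recorded. Item 1 also covers parent APAP, so a fall in adducts alone does not make it negative.

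The per-patient miss rates also overstate the risk for the sub-study as a whole. Take 4 to 8 APAP patients, half-lives of 1.3 to 2.7 days, baselines around 10 or 20 µmol/L (log SD 0.3), daily samples and 1 µmol/L added per dose, all assumed. Item 1 then fires in at least one patient in 75–100% of sub-studies.

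Much of this stands, and it softens the consequence. It does not remove the defect. None of these safeguards gives a benchmark for decline in overdose patients. Item 2 informs about them only if they form adducts from a dose as other patients do, which the documents do not address. In the same setting item 1 also fires in 23–41% of sub-studies with no methacetin effect, so a positive is hard to interpret too.

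A further fair objection concerns the obvious repair, a dosed-minus-undosed contrast. The dose-free intervals are late, while three of the four dosed intervals are early. If elimination slows, the contrast is biased towards no accumulation. At 20 µmol/L with 6 patients, its power falls from 57% to 25% if half-life lengthens by 25% after Day 4. It cannot carry the conclusion alone.

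**Conclusion.** The concern holds in a limited form. Item 1 tests net change against zero, so it does not flag a contribution that only slows the fall, and it can flag patients through assay noise. The logic follows from the text. The size does not: baseline, half-life and assay CV are assumptions, and the 1 µmol/L break-even ranges from about 1.1 to 10.6 µmol/L. The sampling conflict matters at least as much. In the four scenarios above the per-patient miss rate is 84–99% on the 8.5 days against 44–84% with daily samples.

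A reader might infer that each dose could add more than a toxic amount while the sub-study reports no harm. The documents do not support that. They do not show that such a contribution occurs or give the levels needed to judge it. The item 2 figure is a serum level, not an increment per dose, and the synopsis figure for the same group is 1000-fold lower. No passage says that a negative item 1 establishes safety.

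**What to change.** 1. Reconcile 8.5 and 4.2.3 with the daily sampling in 8.3 and 10.1, so that the dose-free intervals Day 4–5 and Day 6–7 are observed.
2. Keep item 1 as a per-patient flag for the Medical Safety Monitor. In 4.2.3 and 12.2.2, base the APAP-ALF conclusion on the estimated within-patient rate of log-adduct decline with a confidence interval, shown separately for dosed and dose-free intervals. Report the dosed-minus-undosed difference as supportive only, with a sensitivity analysis that lets elimination slow over time. State that accumulation is excluded only up to the bound, under that assumption.
3. Reconcile the adduct threshold in 4.2.3 (µmol/L) with that in the synopsis (nmol/L).

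The cost is a few lines of text, one schedule row and one analysis of samples that 8.3 and 10.1 already plan. The drawback is imprecision: few of the 20 patients may have APAP aetiology, and samples will be lost to discharge, transfer, transplant or death.

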### **8.2.1 Requirements for Administration of Test Substrate**

#### 1. Fasting

Subjects will perform the breath test once enrolled into the trial and when the following criteria have been met:

- Protocol-specified labs are completed prior to the administration of the test substrate.
- *Oral administration of test substrate:* The subject should be fasting from solid food for a minimum 6 hours and from oral medications for a minimum of 1 hour.
- *Naso-enteric and orogastric tube administration of test substrate.* In subjects who are receiving tube feeding, feeding should be discontinued for a minimum of 4 hours. Gastric contents should be aspirated prior to the instillation of C-Methacetin solution *via* the naso-enteric or orogastric tube.

Feeding may be resumed after the MBT has been completed (*i.e.*, at 60 minutes after administration of the test substrate).

2. Subject has not ingested acetaminophen-related medications (e.g. Tylenol) within the past 24 hours (subjects with acetaminophen intoxication may be included 24 hours after ingestion).
3. Subject has not received general anesthesia in the last 24 hours. This does not include appropriate utilization of sedative and analgesic drugs for subjects within a critical care

environment, such as propofol sedation or sedation related to liver biopsy. In those instances, all enterally and parenterally administered medications will be recorded in the study CRF.

4. Evidence of ileus or presenting with contra-indication to administration of oral drugs.
5. The MBT should not be performed in cases where there is a suspicion that aspiration may occur.
6. Subjects who require RRT (intermittent and continuous) after enrollment into the study will not be excluded; however, it is preferred that the test substrate and Breath Test are not administered during dialysis treatments.

**Note:** Subjects with gastroparesis may be included as the delayed emptying has negligible impact on fluids (17). The presence of evidence of delayed gastric emptying and/or ileus should be noted on the CRF for further analysis to show that the impact is negligible for MBT measures. Naso-enteric and orogastric tubes should be clamped for 10 minutes after administration of the C-Methacetin solution.

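### Safety endpoint item 2 can be met by the Day 1 sample drawn before any substrate, because it sets no condition on the baseline adduct level

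*Combined protocol and SAP*

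**What the plan says.** Section 4.2.3 defines a positive safety endpoint in three items.

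- Item 1, for APAP overdose, is a change rule: "the absence of decline in APAP or APAP-adduct concentration between two consecutive determinations for patients with ALF due to APAP overdose".
- Item 2, for the other ALF patients, is a level rule. It is met when a toxic quantity, set there at 1 µmol/L or more, is present: "APAP-adducts in patients with non-APAP ALF".
- Item 3 covers "adjudicated cases where APAP (non-adduct, parent compound) is detected in the serum of a patient with non-APAP ALF". These cases go to the "independent Medical Safety Monitor to determine the likelihood of Methacetin toxicity".

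On timing, Section 4.2.3 has serum drawn "immediately prior to each administration of the" substrate. Section 8.3 collects samples on Days 2 to 7 "as well as Day 1 as a baseline value", in the first 20 ALF subjects, and Section 10.1 says the same. Section 8.3 gives the sole purpose of the samples as finding out whether APAP or adducts build up as dosing is repeated.

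The Safety Analysis row of the synopsis repeats the level rule without a baseline: "The detection of serum APAP-Cys adducts in those ALF patients not thought secondary to APAP toxicity will be considered significant" above 1.0 nmol/L. It treats any detectable APAP in these patients the same way.

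Section 8.2.1 restricts earlier acetaminophen use only by this condition for giving the substrate: "Subject has not ingested acetaminophen-related medications (e.g. Tylenol) within the past 24 hours".

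**The concern.** The sub-study asks whether giving methacetin, which is metabolised to acetaminophen, adds acetaminophen or its adducts to the serum of patients with ALF. Only a comparison with the pre-dose state can answer that. Item 2 makes no such comparison, although the pre-dose sample is collected and called a baseline. Read literally, it attributes to the substrate whatever adducts a patient brings to the study.

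At stake is the meaning of a positive case in a group of at most 20 ALF subjects, of whom only the non-APAP part falls under item 2. In so small a group, one patient who was positive before dosing changes the count visibly. Nothing in the definition separates that patient from one whose adducts appeared after dosing.

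**Working it through.** The documents state no event rate, sample size justification or test for this endpoint, so there is no figure of the plan's to reproduce. The check is mainly one of wording.

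**Step 1: can the Day 1 sample precede dosing?** Yes. Section 4.2.3 places sampling before each administration, Sections 8.3 and 10.1 call Day 1 the baseline, and Section 8.2.1 requires the protocol-specified laboratory tests to be finished before the substrate is given.

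**Step 2: does item 2 exclude that sample?** No. It names a population, an analyte and a threshold. It does not mention Day 1, a change, or a sample taken after a dose.

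**Step 3: can a non-APAP patient have had earlier acetaminophen?** The documents allow it. Section 8.2.1 looks back 24 hours only, and the exclusion criteria in Section 6.2 bar allergy to acetaminophen but not earlier use. Whether such use would leave adducts at the toxic threshold is not stated.

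**Step 4: apply the rules to three adduct patterns.** T is the threshold, whichever unit applies.

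| Pattern in one patient | Item 2 as written (non-APAP) | Item 1 rule applied to the same values | New since Day 1? |
|---|---|---|---|
| Day 1 at or above T, then falling at every sample | Positive | Not positive | No |
| Day 1 at or above T, then level or rising | Positive | Positive | No, but no decline |
| Day 1 below T, later at or above T | Positive | Positive where the value rises | Yes |

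The first row shows the defect. A falling series that began before any substrate is a positive endpoint for a non-APAP patient, but would not be one for a patient with APAP overdose. It also shows no accumulation.

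**Step 5: compare with the rest of the protocol.** Section 10.2 defines adverse events as conditions absent before the first dose. Item 1 and the adverse event definition therefore both refer to an earlier state; item 2 does not.

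**Step 6: can the size be given?** Let n be the number of non-APAP patients among the first 20 ALF subjects and p the probability of being at or above T before dosing. The chance of at least one pre-dose positive is 1 − (1 − p)^n. Neither n nor p is in the documents, so both are assumed here:

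| n | p = 1% | p = 5% | p = 10% | p = 20% |
|---|---|---|---|---|
| 5 | 5% | 23% | 41% | 67% |
| 10 | 10% | 40% | 65% | 89% |
| 15 | 14% | 54% | 79% | 97% |
| 20 | 18% | 64% | 88% | 99% |

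For example, n = 10 and p = 5% gives 1 − 0.95^10 = 0.40. The grid runs from 5% to 99%, so it shows that the chance is sensitive to the unknowns and gives no estimate of it. The p needed is the prevalence at or above T, not the prevalence of any detectable adduct.

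The threshold also affects p. Section 4.2.3 gives it in µmol/L and the synopsis in nmol/L, a 1000-fold difference. That is a separate conflict, and the two passages must be reconciled. The missing baseline condition remains whichever unit is kept.

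**The case against.** The strongest reply is that the surrounding text makes the intention plain. Section 8.3 speaks of accumulation, Day 1 is labelled a baseline, and nobody would seriously count a pre-dose value as a methacetin event. A deliberately sensitive trigger followed by expert review is also a legitimate safety design. Part of this stands: the intention is probably a comparison with Day 1. But item 2 is the operative definition and says something else, and no passage explains how the baseline enters it.

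A reader might infer three stronger points that the documents do not support.

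- *That item 3 is equally defective.* Its wording has the same gap, but it counts only adjudicated cases, judged for likely methacetin toxicity. A detection before the first dose would hardly pass that judgement. What remains is that no written rule directs the Monitor to the Day 1 result.
- *That a pre-dose positive could not be told from a true one.* Section 4.2.3 sends adduct results to the Monitor in real time for review, and the Day 1 sample is identifiable. The gap is narrower: item 2 does not depend on that review, and the summary that goes on to the DSMB is not required to separate the two kinds of case.
- *That item 2 relaxes the decision rule of the earlier King's College study.* Section 4.2.3 reports that study's result as no new appearance of adducts, but it also says the sera were tested for presence. It gives a finding, not a decision rule, so no such comparison can be made.

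**Conclusion.** The point holds for item 2 and for the matching adduct sentence in the synopsis. As written, a non-APAP ALF patient can be a positive safety case on the Day 1 pre-dose sample, which runs against the stated purpose of the samples and the form of item 1. This is a rule that misclassifies, not merely a missing detail. For item 3 the gap is minor because of adjudication.

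The frequency is unknown. A reader might take one of the percentages above as the expected false-positive risk; the documents support none of them. It would also go too far to infer damage to the trial's main result. The issue is confined to the safety sub-study, no test or stopping rule is attached to this endpoint, and the Day 1 PDR peak analysis is untouched. The conclusion rests on reading item 2 literally and on the Day 1 sample being drawn before the substrate, as Section 4.2.3 specifies. The change should be made because it is cheap and the endpoint is otherwise ambiguous.

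**What to change.** - **Item 2:** define a positive case as adducts below the threshold in the Day 1 pre-dose sample and at or above it in a later sample.
- **Patients at or above the threshold on Day 1:** report them on a separate line and assess them with item 1's existing rule, absence of decline between consecutive determinations. They stay under safety review and have a defined criterion.
- **Item 3:** keep adjudication of every detection, and have the Monitor record whether APAP was already detected on Day 1. Do not label such patients as exposed, because Section 4.2.3 warns that high bilirubin can produce false-positive APAP results in some assays.
- **Synopsis, Safety Analysis:** align the text with these definitions.

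The cost is a change of wording. The Day 1 sample is already planned, so no visit, draw or assay is added. The small downside is that patients positive on Day 1 leave the denominator for new appearance; both numbers should be reported.
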